11.4.4. Efficacy

Microbiology Procedures

 • Microbiology data will be received from below sources: 
 • GSK microbiologists • Central laboratory • 3rd party laboratory
CCI

 • All gram-negative uropathogens will be tested by broth microdilution (MIC) to determine production of extended spectrum beta-lactamases (ESBLs). In accordance with the Clinical and Laboratory Standards Institute (CLSI) M100 guidelines (Table3A), ESBL production may be indicated by a MIC result of >1 mcg/mL for ceftriaxone ceftazidime, cefotaxime or aztreonam for E. coli, K. pneumoniae or K. oxytoca or a MIC result of >1 mcg/mL for ceftazidime, cefotaxime or cefpodoxime for P. mirabilis. • Gradient diffusion results (MIC) on all uropathogens for susceptibility to gepotidacin • Gradient Diffusion MICs and Interpretation 
 • Gradient diffusion strips generate MIC values from a continuous scale and can give results in-between conventional two-fold dilutions i.e. half dilutions. A gradient diffusion MIC value which falls between standard two-fold dilutions must be rounded up to the next upper two-fold value before categorization. • As an example, a gradient diffusion MIC of 1 ug/mL is reported as intermediate (I) while 1.5 is rounded up to 2 ug/mL and the category reported as resistant (R). • When growth occurs along the entire strip i.e. no inhibition ellipse is seen, report the MIC as >= the highest value on the MIC scale. When the inhibition ellipse is below the strip (does not intersect the strip), report the MIC < the lowest value on the MIC scale. • MIC Reporting Concentrations 
 • When serial two-fold dilution MICs are being prepared and tested, the actual dilution scheme is, e.g.: 16, 8, 4, 2, 1, 0.5, 0.25, 0.125, 0.0625, 0.03125, 0.015625, 0.0078125 ug/ml, etc.

Microbiology Procedures

- For convenience only, it was decided to use the following values for reporting purpose (reporting format): 16, 8, 4, 2, 1, 0.5, 0.25, 0.12, 0.06, 0.03, 0.016, 0.008, 0.004, 0.002 ug/mL, etc. The values that appear in the Tables are equivalent to the actual values tested, e.g., 0.12 ug/mL = 0.125 ug/mL; 0.016 ug/ml = 0.015625 ug/ml.
- Any values containing '<', '<=', '>=', '>' will be counted in its separate categories. However, when calculating the minimum, maximum, MIC₅₀, MIC₉₀, a small amount will be added or subtracted in order to impute the corresponding numeric value for calculation. For example,
 - '<0.06' will be imputed as 0.06-0.001;
 - '>256' will be imputed as 256+0.001.
 - '>=32' will be imputed as 32.
- But for reporting, they will still be presented in original format if they happen to be those summary statistics.
- Disk Diffusion results (mm) will be conducted on uropathogens as follows. CLSI interpretive criteria are applied with the exceptions of nitroxoline and cefadroxil where EUCAST interpretive criteria are applied.

Compound	Organisms
Gepofidacin ^a	All uropathogens
Nitroxoline ^b	All uropathogens
Nitrofurantoin	All uropathogens
Mecillinam ^{c,d}	Gram-negative uropathogens
Cefadroxil ^b	Gram-negative uropathogens
Penicillin	Staphylococci (S. aureus and S. saprophyticus) and enterococci uropathogens
Cefoxitin ^b	Staphylococci uropathogen isolates (S. aureus and S. saprophyticus)

- a. Two manufacturers (Becton Dickinson and MAST)
- b. To be tested by disk diffusion (surrogate test or no MIC QC ranges)
- c. To be tested by disk diffusion (broth method not approved and gradient diffusion is not available)
- d. Tested to predict the activity of pivmecillinam

- The 3rd party laboratory will conduct confirmatory nitrofurantoin susceptibility testing, agar dilution testing for fosfomycin and genetic characterization of selected isolates as described directly below.
 - Uropathogens exhibiting intermediate or resistant (with the exception of species considered intrinsically resistant to nitrofurantoin per CLSI M100 guidelines) nitrofurantoin MIC results at the central laboratory will be submitted to the 3rd party laboratory for confirmatory susceptibility testing of nitrofurantoin (dilution range of 2–256 µg/mL) by reference broth microdilution. Broth microdilution nitrofurantoin MIC from JMI Laboratories (if available) will take precedence over global central laboratory (GCL) nitrofurantoin MIC result for determining susceptibility to nitrofurantoin.
 - All uropathogens will be submitted for susceptibility testing of fosfomycin (dilution range of 0.12–256 mcg/mL) by reference agar dilution methodology.

Microbiology Procedures

CCI

Microbiology Procedures
Microbiological Data Procedures

 • PPD global central laboratory (GCL) will identify the uropathogen classification and phenotype via GSK source documents regarding qualified uropathogen flagging and uropathogen resistance flagging (Uropathogen and qualifying uropathogen decision tree_112119_GSK final.docx and GSK Uropathogen resistance decision trees_112119_final.docx). • JMI laboratories genotype data is derived from isolate whole genome sequencing and other genomic assays as requested by GSK and will be performed by JMI when a minimum of 20 isolates are available but not more frequent on a monthly basis (testing may be conducted more frequently near the end of the study). Genotype data therefore will be available no sooner than 1-2 months from isolate recovery. • JMI isolate genotype data will be sent to PPD GCL and included in PPD GCL data transfers to PPD clinical and therefore available for PPD Biostatistics and PPD clinical programing for inclusion in analysis database. • Data from the GSK study microbiologist/or clinical scientist will include clarification of which uropathogen species should be reported separately and which should be grouped for display, classification of uropathogens as Gram-positive or Gram-negative, determination of the phenotype and genotype subcategories and a determination of whether the susceptibility results for identically labelled uropathogens from the same participant at the same visit differ enough to classify the uropathogens as separate (“keepers”). 
“Keepers” process
 
 • Includes all cases within the central laboratory dataset where two or more uropathogens of the same genus and species for the same participant at the same visit will be identified. • An excel file containing a list of these uropathogens and the associated quantitative bacterial counts, MIC results and CLSI interpretations for each isolate will be provided to the microbiologist. 
 • The microbiologist will review the list and determine if the isolates are the same or different strains of the identified uropathogen based on a predefined algorithm: 
 ▪ For example, if two uropathogens of the same genus and species have a ≥ 4-fold difference in MIC (or ≥ 6 mm difference in zone diameter for antibiotics only tested by disk) to three or more antibiotic classes, they will be considered two different strains and both uropathogen isolates will be analyzed. • If none of the criteria for determining the isolates as different are met, the uropathogen isolates will be considered to be of the same strain and only one isolate will be retained for analysis based on a pre-defined algorithm.

- The microbiologist will add a flag to the list to indicate which of the duplicate records to keep (flag = >0; e.g. 1, 2). All duplicate records will be kept in the SDTM datasets, and those records that are deemed to be duplicates (flag = 0) will not be included in any analyses.

Microbiological outcome and response in instances of 2 baseline qualifying uropathogens

- If two baseline qualifying uropathogens are recovered that are of two different genus and species (e.g. a *K. pneumoniae* and *E. coli*), each baseline uropathogen will be considered separately for microbiological outcome and response.
- If more than one baseline qualifying uropathogen is recovered that are of the same genus and species (e.g. two morphotypes of *E. coli*) and if the same genus and species is recovered from a post-baseline visit, the microbiological outcome and response will not be linked to the baseline uropathogen (i.e., genetic relatedness of the baseline and post-baseline isolates will not be considered for determination of microbiological outcome/response). For these cases, the microbiological outcomes will be either persistence, recurrence or unable to determine (e.g. if other antibiotic therapy started before TOC) and the microbiological response will be failure for both baseline qualifying uropathogens of the same species.

Uropathogen species/groups; Gram-positive/-negative classification; phenotype and genotype sub-categories flagging:

- A summary for the number of isolates in each distinct uropathogen species (by decoded uropathogen code, phenotypic and genotypic data) for uropathogens at Baseline will be produced for the microbiologist.
- The microbiologist and clinical scientist will review that summary to flag those uropathogen species/groups, Gram-positive/-negative classifications, and phenotype and genotype uropathogen subcategories(s) which are to be reported in the TLFs.

Invalid and non-evaluable results

- In rare cases of concern about the integrity of a subject(s) urine sample, the microbiologist or clinical scientist may determine that all microbiological assessments done on that urine sample are invalid and non-evaluable. Potential reasons include evidence of sample mishandling and cross-contamination.

CCI

- These invalid records will be kept in the SDTM dataset but not ADaM dataset and will not be included in any analyses.
- The microbiologist will document the rationale for invalid results and store in a similar manner along with the rationale for the keepers analyses.

Out of stability (OOS)

- GCL will include an out of stability (OOS) flag for urine samples that are received OOS. OOS urine samples are those where receipt date is more than 4 days from the specimen collection date for urine specimens sent refrigerated, and those where receipt date is more than 2 days from the specimen collection date for urine specimens sent ambient. Samples received frozen are marked as 'unable to perform' and are not tested. All microbiological assessments done on the OOS urine sample are invalid and non-evaluable.
- These OOS samples will be kept in SDTM dataset but not ADaM dataset and will not be included in any analyses.

Fold Change

- Fold change will be used to describe how much the MIC for gepotidacin and nitrofurantoin changes between baseline and subsequent visits for the same bacterial species from the same participant.
- Fold change will be calculated (in doubling dilutions) as the ratio of the MIC at the subsequent visit to the MIC at Baseline Visit. However, ratio of 1 will be reported as 0-fold. Ratio less than 1 will be reported in reciprocal with negative sign (e.g. ratio of 0.5 will be reported as -2-fold). Examples:

Baseline MIC (mcg/mL)	Post-baseline MIC (mcg/mL)	Fold-change
1	1	0-fold
1	2	2-fold
1	4	4-fold
1	8	8-fold
1	16	16-fold
1	0.5	- 2-fold
1	0.25	- 4-fold
1	>32	>/=64-fold
1	>/=32	>/=32-fold
1	<0.125	>/= - 16-fold
1	</=0.125	>/= - 8-fold

MIC Range, MIC50 and MIC90	

MIC50 and MIC90 are defined as the 50th and 90th percentile of the MIC values. They will only be reported if sample size is larger or equal to 10. For an even number of samples, the MIC50 is the next one above the median. Similar algorithm applies to MIC90.
	

 MIC ranges to be tested in this protocol (in ug/mL): 	
Gepotidacin	<=0.03; 0.06; 0.12; 0.25; 0.5; 1; 2; 4; 8; 16; 32; 64; >64
Ciprofloxacin	<=0.002; 0.004; 0.008; 0.015; 0.03; 0.06; 0.12; 0.25; 0.5; 1; 2; 4; >4
Levofloxacin	<=0.004; 0.008; 0.015; 0.03; 0.06; 0.12; 0.25; 0.5; 1; 2; 4; 8; >8
Sulfisoxazole	<=4; 8; 16; 32; 64; 128; 256; 512; >512
Trimethoprim	<=0.015; 0.03; 0.06; 0.12; 0.25; 0.5; 1; 2; 4; 8; 16; 32; >32
Trimethoprim / Sulfamethoxazole	<=0.015; 0.03; 0.06; 0.12; 0.25; 0.5; 1; 2; 4; 8; >8
Ampicillin	<=0.25; 0.5; 1; 2; 4; 8; 16; 32; 64; >64
Vancomycin	<=0.25; 0.5; 1; 2; 4; 8; 16; 32; >32
Nitrofurantoin	<=0.5; 1; 2; 4; 8; 16; 32; 64; 128; 256; >256
Ceftolozane / Tazobactam	<=0.015; 0.03; 0.06; 0.12; 0.25; 0.5; 1; 2; 4; 8; 16; 32; >32
Ceftazidime / Avibactam	<=0.015; 0.03; 0.06; 0.12; 0.25; 0.5; 1; 2; 4; 8; 16; 32; >32
Piperacillin / Tazobactam	<=0.12; 0.25; 0.5; 1; 2; 4; 8; 16; 32; 64; 128; >128
Amoxicillin / Clavulanic Acid	<=0.25; 0.5; 1; 2; 4; 8; 16; 32; >32
Ceftriaxone	<=0.015; 0.03; 0.06; 0.12; 0.25; 0.5; 1; 2; 4; >4
Cefazolin	<=0.25; 0.5; 1; 2; 4; 8; 16; 32; >32
Meropenem	<=0.004; 0.008; 0.015; 0.03; 0.06; 0.12; 0.25; 0.5; 1; 2; 4; 8; >8
Gentamicin	<=0.06; 0.12; 0.25; 0.5; 1; 2; 4; 8; 16; >16
Amikacin	<=0.25; 0.5; 1; 2; 4; 8; 16; 32; 64; >64
Aztreonam	<=1; >1
Ceftazidime	<=1; >1
Cefotaxime	<=1; >1
Cefpodoxime	<=1; >1
Fosfomicin (JMI)	<=0.12; 0.25; 0.5; 1; 2; 4; 8; 16; 32; 64; 128; 256; >256
Nitrofurantoin (JMI)	<=0.5; 1; 2; 4; 8; 16; 32; 64; 128; 256; >256
Gepotidacin Gradient Strip	<0.015; 0.03; 0.06; 0.12; 0.25; 0.5; 1; 2; 4; 8; 16; 32; 64; 128; 256; >=256

Susceptibility Interpretations

 • Susceptibility interpretations will be calculated and reported by the central laboratory and will be based on the CLSI M100 and EUCAST guidelines in effect at that time the bacterial isolate is tested. • Since CLSI breakpoints for certain drug/bug combinations can change in new yearly editions of M100 guidelines, as GSK and/or the central laboratory become aware of relevant breakpoint changes, the central laboratory will identify any reports which would qualify as needing a change in interpretation (e.g. a MIC value that was originally reported as susceptible, and would now be considered resistant based on the new breakpoint), and will issue amended reports. Of note, for piperacillin/tazobactam against Enterobacterales species/groups, susceptible-dose dependent (SDD) may be presented as intermediate • The final clinical database will report interpretations according to the most recent CLSI M100 and EUCAST interpretations regardless of what the breakpoints were at the time the isolate was initially tested. • For specific drugs (e.g. nitroxoline, cefadroxil) which do not have approved FDA or CLSI breakpoints, susceptibility interpretations will be determined using EUCAST guidelines.
Bacterial Nomenclature

 • Whilst the scientific formatting requirements for bacterial nomenclature is for genus and species names to be italicized, with first letter of genus upper case, and rest of the genus and species name in lower case, GSK system limitations have resulted in the lack of italicization in TFL outputs.
CCI
Quantitative Bacterial Counts

 • The central laboratory will quantitatively determine the growth of uropathogens from culture of participant urine samples. • The central laboratory will report the following quantification results 
 • If there is no growth on the culture plates for a urine sample: 
 ▪ No growth (<10³) • If there is growth on the urine culture plates for a urine sample, each uropathogen will receive an associated colony count: 
 ▪ 10³-<10⁴ ▪ 10⁴-<10⁵ ▪ ≥10⁵ • At subsequent visits, determination of 'no growth' for individual uropathogens will need to be derived from an overall urine culture result of no growth (meaning there was no growth on the urine culture plates) or no identification/quantification being reported for that specific uropathogen (assuming that a urine sample was taken and that results were reported). • If the bacterial sample at a subsequent visit is not collected, then it's considered as "unable to determine" for the uropathogens identified at Baseline.

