5.5. Multiple Comparisons and Multiplicity

The primary comparison of interest is the comparison between gepotidacin to nitrofurantoin for the primary endpoint of therapeutic response rate at TOC in the micro-ITT NTF-S Population. This analysis will be adjusted for stratification factors. The issue of multiple comparisons in the primary analysis will be addressed by testing the noninferiority of gepotidacin to treatment with nitrofurantoin prior to testing for superiority as described in Section 2.4. Further to this, the IA recommendation framework is defined per Figure 3. The IA recommendation framework required that both the noninferiority criteria is met in both the primary analysis population and the supplementary population for the study to be stopped for efficacy and noninferiority to be declared. Note: If the study continues at the interim, demonstration of NI at the final analysis will remain based on the primary analysis only (micro-ITT NTF-S) and the

supplementary analysis (micro-ITT NTF-S (CAPA)) performed at the final analysis will be provided for descriptive purposes only.

Figure 3 Study Success Definition and IA Recommendation Framework

1. Note: Only the micro-ITT NTF-S population will be used to determine if the futility boundary has been met. The micro-ITT NTF-S (CAPA) analysis will also be available to the IDMC for consideration.
2. Note: If there is not sufficient microbiology data the IDMC will perform the IA for futility with a planned sample size of 768 rather than 884
3. Note: For the interim analysis, the efficacy evidence used to stop or continue a study is based on the noninferiority testing only, i.e. not superiority testing.
4. Note: The supplementary analysis at the EOS may exclude more investigators/sites than the supplementary analysis at the IA

The statistical analyses of all other efficacy endpoints will be descriptive in nature, and therefore, will not be subject to multiplicity adjustments.

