aac(3)-IIa	18/25 (72.0)	21/31 (67.7)	4.3 (-22.0 to 28.7)
β-Lactamase-gene positive ^d	62/80 (77.5)	53/81 (65.4)	12.1 (-2.8 to 26.2)
bla _{CTX-M-15}	39/48 (81.3)	36/50 (72.0)	9.3 (-9.0 to 26.7)
bla _{OXA-1/OXA-30}	31/42 (73.8)	27/40 (67.5)	6.3 (-14.7 to 26.8)
^a Microbiological eradication defined as a reduction in baseline pathogen from $\geq 10^5$ CFU to $< 10^4$ CFU in urine culture. ^b AG-NS defined as nonsusceptible interpretation (intermediate or resistant) to any of amikacin, gentamicin, or tobramycin based on central laboratory MIC testing and Clinical and Laboratory Standards Institute 2016 breakpoints. ^c ESBL phenotype defined as MIC ≥ 2 $\mu\text{g}/\text{mL}$ to any of ceftazidime, aztreonam, or ceftriaxone based on central laboratory testing. ^d All isolates with AG-NS and ESBL phenotypes were sequenced for both AME and ESBL genes. N, number of patients in the specified population; N1, number of uropathogens in the specified category at baseline; n, number of uropathogens eradicated in the specified category. CFU, colony forming units; CI, confidence interval; ESBL, extended-spectrum β-lactamase; MIC, minimum inhibitory concentration; MIC _{50/90} , minimum inhibitory concentration required to inhibit the growth of 50%/90% of organisms; mMITT, microbiological modified intent-to-treat; NS, nonsusceptible; TOC, test of cure.			

Note: Uropathogen genotypic subcategories may be reported individually (e.g. *bla*_{CTX-M-15}) or grouped together (e.g. ESBL-gene positive) for reporting, dependent on numbers recovered and epidemiological significance. See examples above. The potential individual and group categories will be monitored in stream during the study and provided by the GSK microbiology team.

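### The even-sample rule can put MIC50 above the concentration that already inhibits half the isolates, and MIC90 has no stated formula

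*SAP*

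**What the plan says.** The rule is in SAP 11.4.4 (Efficacy), under the sub-heading on MIC range, MIC50 and MIC90. The definition is "MIC50 and MIC90 are defined as the 50th and 90th percentile of the MIC values". A size floor follows: "They will only be reported if sample size is larger or equal to 10". The handling of even group sizes is "For an even number of samples, the MIC50 is the next one above the median", and the only instruction for the other summary is "Similar algorithm applies to MIC90". No rank or formula is given for either.

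The values lie on a two-fold dilution grid; for gepotidacin it is "<=0.03; 0.06; 0.12; 0.25; 0.5; 1; 2; 4; 8; 16; 32; 64; >64". When a censored value turns out to be the summary statistic, the same section says: "But for reporting, they will still be presented in original format if they happen to be those summary statistics". The plan therefore expects MIC50 and MIC90 to be observed MIC categories, not averages of two values.

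**The concern.** MIC50 and MIC90 are the usual one-number summaries of potency, and a reader takes them as the concentration at which half, or nine tenths, of the isolates are inhibited. For even n the (n/2)-th ordered MIC already meets that requirement for MIC50, yet the rule moves past it. The departure can only be upward, so it can only understate potency. It matters most just above the floor of 10 isolates. SAP 5.4.2 plans efficacy summaries by uropathogen species or group and by phenotypic and genotypic subcategory, where small groups are likely.

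The wording also allows more than one program. The value above the median may mean the next rank or the next distinct MIC, and MIC90 is left to the programmer. Two analysts could report different values from the same isolates.

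**Working it through.** The plan gives no numerical result to reproduce, so the check compares ordered values.

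**Ranks.** The lowest observed MIC that inhibits at least 50% of n isolates has rank ceil(0.5n); for 90% it is ceil(0.9n). On the next-rank reading the SAP gives n/2+1 for MIC50 when n is even. For MIC90 I read the similar algorithm as 0.9n+1 when 0.9n is whole, and ceil(0.9n) otherwise. That is an inference, because the SAP does not state it.

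| n | MIC50 rank: lowest that suffices / SAP | MIC90 rank: lowest that suffices / SAP as inferred |
|---|---|---|
| 10 | 5 (50%) / 6 (60%) | 9 (90%) / 10 (100%) |
| 11 | 6 / 6 | 10 / 10 |
| 12 | 6 (50%) / 7 (58.3%) | 11 / 11 |
| 20 | 10 (50%) / 11 (55%) | 18 (90%) / 19 (95%) |
| 100 | 50 (50%) / 51 (51%) | 90 (90%) / 91 (91%) |

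Percentages are isolates inhibited at that rank if there are no ties. MIC50 moves for every even n; MIC90 moves only when n is a multiple of 10.

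**Middle values differ.** Take MICs 0.5, 0.5, 1, 1, 1, 2, 2, 2, 4, 8.
- At 1 µg/mL, 5 of 10 are inhibited. The SAP rule reports 2, which inhibits 8 of 10.
- At 4 µg/mL, 9 of 10 are inhibited. The inferred MIC90 rule reports 8, the maximum.

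**Middle values tied.** Take MICs 0.5, 1, 1, 2, 2, 2, 2, 2, 4, 4.
- Next rank: ranks 5 and 6 are both 2, and ranks 9 and 10 are both 4, so nothing changes.
- Next distinct value: the median is 2 and the next MIC above it is 4. But 8 of 10 isolates lie below 4, so 4 is not a 50th percentile under any convention.

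The two readings agree when the middle values differ and part when they are tied.

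**How often the next-rank reading changes the result.** This needs an MIC distribution, which the documents do not give. Assumption: log2 MIC is normal, rounded up to the two-fold grid, with its centre uniform within one dilution step; 40,000 simulated groups per cell. Entries are the share of groups in which the reported value rises.

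| n | SD (dilutions) | MIC50 | MIC90 |
|---|---|---|---|
| 10 | 1 / 1.5 / 2 | 24.4% / 34.8% / 43.6% | 47.6% / 60.5% / 68.4% |
| 20 | 1 / 1.5 / 2 | 12.4% / 18.3% / 24.4% | 27.3% / 38.6% / 47.6% |
| 100 | 1 / 1.5 / 2 | 2.5% / 3.7% / 5.0% | 5.9% / 8.6% / 11.4% |

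At n=10 the mean upward shift, counting groups with no change as zero, is 0.25 to 0.49 doubling dilutions for MIC50 and 0.54 to 1.08 for MIC90. With a narrower SD of 0.75 the n=10 shares are 17.9% and 38.1%. Placement matters in larger groups: with the true median exactly on a dilution boundary, the MIC50 share at n=100 is about 8%.

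**The case against.** The best defence is that, under the SAP's percentile definition, any value from rank n/2 to rank n/2+1 is a valid 50th percentile. Choosing the upper one is a pre-specified convention that returns an observed MIC and cannot flatter gepotidacin. This stands for the next-rank reading, which is an admissible choice and not an arithmetic error. It does not rescue the next-distinct reading, and it does not supply the missing MIC90 rule.

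Four stronger inferences are tempting, and the documents do not support them.

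- **That the SAP contradicts its own definition.** SAP 11.12 does contain the phrase "minimum inhibitory concentration required to inhibit the growth of 50%/90% of organisms". It is an abbreviation footnote to a table reproduced as an example output from a published study of other drugs. It shows the usual meaning of the term but is not a definition adopted for this trial.
- **That the reported value is always too high.** On a two-fold grid ties are common. Under the assumptions above, MIC50 is unchanged in about 56% to 76% of groups of 10, and almost always in large groups.
- **That treatment arms or drugs cannot be compared.** The same rule applies to all drugs. Where two drugs are summarised over the same isolates, the same rank is compared. Only groups of different size can be treated differently.
- **That the trial's conclusions are at risk.** SAP 5.5 states: "The statistical analyses of all other efficacy endpoints will be descriptive in nature, and therefore, will not be subject to multiplicity adjustments". Entry to the nitrofurantoin-susceptible population uses each isolate's MIC interpretation (SAP Section 4), not MIC50 or MIC90.

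Many efficacy displays are redacted, so whether full MIC distributions accompany these summaries cannot be checked.

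**Conclusion.** The concern holds as a minor defect of specification with a one-way effect. For even n the next-rank reading passes over a value that already inhibits 50% of isolates. On the natural reading of the MIC90 instruction, a group of exactly 10 has its maximum reported as MIC90, so a single resistant isolate can set it. The literal next-distinct reading can leave the percentile definition altogether.

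The rank results are exact, apart from the inferred MIC90 rank. The frequencies depend on the assumed normal log2 MIC, its spread and the random centre; they are largest at n=10 and small by n=100. A change is usually one doubling dilution, but can be more where the distribution is split or has an outlier.

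**What to change.** Replace the even-sample sentence and the MIC90 sentence in SAP 11.4.4 with a single rule: MIC50 and MIC90 are the lowest observed MICs at which the cumulative percentage of isolates inhibited is at least 50% and at least 90%, that is, the ceil(0.5n)-th and ceil(0.9n)-th ordered values, for odd and even n alike.

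At n=10 this gives ranks 5 and 9, at n=12 ranks 6 and 11, and at n=20 ranks 10 and 18; odd n is unchanged. It always returns an observed MIC, so it fits the existing presentation of censored values. If the sponsor prefers the upper middle value, the SAP should state that rank, and the MIC90 rank, explicitly.

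The cost is one SAP sentence and one line of code.
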